Clinical Trial Protocol

Clinical Evaluation of Venus Versa Diamondpolar Applicator Treatment Followed by AC Dual Applicator
Treatment Using Two Intense Pulsed Light Wavelength Bands for Facial Acne Vulgaris

Sponsor: Venus Concept
Version Date: April 4, 2017
Amendment 2
Protocol number CS2715

Sponsor Contact

- [name]
Director of Clinical Research
- [contact] [name]
- E-mail: [contact]
- Address: Venus Concept Ltd. [name]

Signature of Sponsor Representative

05 / Apr / 2017

Date: (DD/MMM/YYYY)

STATEMENT OF CONFIDENTIALITY

The information contained herein is Confidential Information that remains the sole and exclusive property of Sponsor and is expressly subject to the terms and conditions of the Clinical Trial Research Agreement signed by both the Investigator and Venus Concept Ltd.,
Toronto, Canada.

Study Synopsis

Study Title	Clinical Evaluation of Venus Versa Diamondpolar Applicator Treatment Followed by AC Dual Applicator Treatment Using 2 Intense Pulsed Light Wavelength Bands for Facial Acne Vulgaris	
Protocol No.	CS2715	
Device Name	Venus Versa device	
Study design	Multi-center, prospective, open label with before-after study design. Each subject will receive 4 full treatments at 1 week intervals. Follow up will take place 6 weeks after the last treatment.	
Projected Study period	Initiation Date: September 2016	Completion Date: December 2017
Study population	Up to 50 healthy subjects, age 18 to 55 years with Acne Vulgaris who wish to improve their skin appearance will be enrolled in order for 20 subjects to complete with the adjusted (amendment 2) treatment parameters.	
Investigational treatment	The procedure will include an (MP) ² (Multi Polar RF & Magnetic Pulse) treatment followed by intense pulse light treatment or intense pulse light treatment alone.	
Study Duration	Each subject will participate in the study for up to 11 weeks (consultation to final follow up). Total study duration is estimated to be 16 months from enrollment of the first subject to the termination visit of the last subject.	
Main Inclusion Criteria:	
 • Healthy Female/Male, age 18 to 55 years with all Fitzpatrick skin phototype. • Having mild to moderate acne vulgaris (as defined by the Acne Global Severity Scale) and have at least 10 inflammatory and 15 non-inflammatory lesions, but no nodulo-cystic lesions. • Subject who can commit to all treatments and follow up. 	
Main Exclusion Criteria:	
 • Superficial metal or other implants in the treatment area. • Current or history of cancer, or current condition of any type of cancer, or pre-malignant moles. • Pregnancy and nursing. • Patients with cystic acne, acne conglobata, acne fulminans, or secondary acne (chloracne, drug-induced acne, etc) • Diseases which may be stimulated by light at the wavelengths used, such as history of Systemic Lupus Erythematosus, Porphyria, and Epilepsy. • Patients with history of diseases stimulated by heat, such as recurrent Herpes Simplex in the treatment area, may be treated only following a prophylactic regimen. • Poorly controlled endocrine disorders, such as Diabetes or Polycystic Ovary Syndrome. • Any active condition in the treatment area, such as sores, Psoriasis, eczema, and rash. • Tattoos, scars or piercings in the treated area. • History of skin disorders, keloids, abnormal wound healing, as well as very dry and fragile skin. 	

	
 • Use of medications, herbs, food supplements, and vitamins known to induce photosensitivity to light exposure at the wavelengths used, such as Isotretinoin (Accutane) within the last six months, tetracyclines, or St. John's Wort within the last two weeks. • Any surgical procedure in the treatment area within the last three months or before complete healing. • Treating over tattoo or permanent makeup. • Excessively tanned skin from sun, tanning beds or tanning creams within the last two weeks. • As per the practitioner's discretion, refrain from treating any condition which might make it unsafe for the patient. • Exposure to investigational product within 3 months (or designated half-life) prior to enrollment. • Prior drugs, interventions, skin laser/light or another device for Acne treatment within 3 months of initial treatment or during the course of the study.

Objectives
	
Primary objectives
 
 • To evaluate the efficacy of facial acne vulgaris treatment using the Venus Versa (MP)² Diamondpolar applicator in combination with the Venus Versa AC dual applicator using two Intense Pulsed Light Wavelength Bands • To evaluate the efficacy of facial acne vulgaris treatment of the Venus Versa AC dual applicator using two Intense Pulsed Light Wavelength Bands. 
Secondary objectives
 
 • To evaluate subject's assessment of improvement & satisfaction. • To evaluate subject's assessment of comfort with the treatments. • To compare the efficacy of the combination treatment and IPL treatment alone.

Hypothesis
	
Both the combination treatment and the IPL treatment will result in Acne Vulgaris improvement. Improvement will be defined as achieving improvement of at least 2 points on the 5-point Global Acne Assessment Score (GASS) at FU (6 weeks following the last treatment) as compared to baseline.

Criteria for Evaluation
	
Efficacy
 
Primary endpoint:
 
 • Acne Vulgaris improvement by at least 2 points on the Global Acne Assessment Score (GASS) from photographs 6 weeks following the last treatment - FU, as compared to baseline, based on before/after photos, as determined by up to 3 independent reviewers (dermatologists and/or plastic surgeons). 
Secondary endpoints: Subject Evaluation, Comfort & Satisfaction
 
 • Reduction of inflammatory lesions and non-inflammatory lesions as determined by investigator based on lesion count. • Improvement in subject satisfaction assessment scale with treatment outcome based on a 5-point Likert scale. • Improvement in subject self-assessment of Acne Vulgaris according to the Global Aesthetic Improvement Scale (GAIS) from photographs 6 weeks following the last

	
treatment - FU, as compared to baseline, based on before/after photos.
 
• Subject assessment of pain and discomfort associated with treatments using a 100 mm Visual Analogue Scale (VAS), where 0 is "no pain" and 10 is "intolerable pain".• Subject improvement assessment of "quality of life" using an acne related Quality of Life (QOL) questionnaire. 
Safety
 
• Evaluate the safety of the treatment by recording the number and type of any adverse event recorded throughout the study. Adverse events will be reported and categorized based on severity and device-relatedness.
--	---

Table of Contents

1	INTRODUCTION	8
1.1	BACKGROUND	8
1.2	RATIONALE FOR THE STUDY.....	10
2	THE INVESTIGATIONAL DEVICE	10
2.1	VENUS VERSA MODULE	11
2.2	AC DUAL APPLICATOR.....	11
2.3	(MP) ² DIAMOND POLAR APPLICATOR.....	11
3	STUDY DESIGN	11
3.1	PRIMARY EFFECTIVENESS ENDPOINT	12
3.2	SECONDARY EFFECTIVENESS ENDPOINTS	12
3.3	SAFETY	13
3.4	STUDY DURATION:.....	13
3.5	SCHEDULE OF TIMES AND EVENTS	13
3.6	CONCURRENT CONTROL	14
3.7	BLINDING.....	15
4	STUDY POPULATION AND SUBJECT SELECTION	15
4.1	SOURCE AND SAMPLE SIZE.....	15
4.2	ELIGIBILITY	15
4.3	SUBJECT WITHDRAWAL AND REPLACEMENT	16
5	STUDY PROCEDURES	17
5.1	SCREENING VISIT	17
5.2	TREATMENT VISITS	18
5.3	FOLLOW-UP VISITS.....	22
5.4	TERMINATION VISIT	23
6	ENDPOINT EVALUATIONS.....	24
6.1	EFFICACY	24
6.2	SUBJECT SELF-ASSESSMENT	24
6.3	SAFETY	25
6.4	SUBJECT DISCOMFORT EVALUATION.....	25
7	STUDY ANALYSIS PLAN.....	26
7.1	STATISTICAL AND ANALYTICAL PLANS.....	26

7.2	STUDY HYPOTHESIS	26
7.3	SAMPLE SIZE JUSTIFICATION	26
7.4	STUDY ANALYSIS	26
8	ADVERSE EVENTS	27
8.1	ADVERSE EVENTS DEFINITIONS	27
8.2	REPORTING	29
8.3	RISK/ BENEFIT ANALYSIS	30
9	ADMINISTRATIVE PROCEDURES	30
9.1	INVESTIGATOR SELECTION	30
9.2	ETHIC COMMITTEE APPROVAL	30
9.3	CASE REPORT FORMS/DATA COLLECTION	31
9.4	REQUIRED DOCUMENTATION	31
9.5	DEVICE USE/ACCOUNTABILITY	31
9.6	TRAINING REQUIREMENTS	31
9.7	MODIFICATION OF PROTOCOL	32
9.8	DATA RETENTION/ARCHIVING DATA	32
9.9	SITE MONITORING	32
9.10	TERMINATION OF STUDY	32
9.11	REPORTING REQUIREMENTS	33
10	REFERENCES	34
11	ABBREVIATIONS AND TERMS	35

List of Tables

Table 1: Study Procedures - CS2715	14
Table 2: Treatment Parameters as per Fitzpatrick Skin Type	20

List of Figures

Figure 1: Study Design	13
Figure 2: Visual Analog Scale	26

INTRODUCTION

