4.1 Source and Sample Size

Up to 50 subjects with all skin phototypes shall be recruited by the investigator from within the investigator's subject population. Subjects shall have mild to moderate acne vulgaris with at least 10 inflammatory and 15 non-inflammatory lesions, but no nodulocystic lesions.

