4.2 Eligibility

Each subject will be evaluated by the Investigator to assess his/her suitability for entry into this study according to the following criteria:

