4.2.2 Exclusion Criteria

Any of the following will exclude the subject from the study:

1. Superficial metal or other implants in the treatment area.
2. Current or history of cancer, or current condition of any type of cancer, or pre-malignant moles.
3. Pregnancy and/or nursing.

4. Diseases which may be stimulated by light at the wavelengths used, such as history of Systemic Lupus Erythematosus, Porphyria, and Epilepsy.
5. Patients with history of diseases stimulated by heat, such as recurrent Herpes Simplex in the treatment area.
6. Poorly controlled endocrine disorders, such as Diabetes or Polycystic Ovary Syndrome.
7. Any active condition in the treatment area, such as sores, Psoriasis, eczema, and rash.
8. History of skin disorders, keloids, abnormal wound healing, as well as very dry and fragile skin.
9. Use of medications, herbs, food supplements, and vitamins known to induce photosensitivity to light exposure at the wavelengths used, such as Isotretinoin (Accutane) within the last six months, tetracyclines, or St. John's Wort within the last two weeks.
10. Any surgical procedure in the treatment area within the last three months or before complete healing.
11. Excessively tanned skin from sun, tanning beds or tanning creams within the last two weeks.
12. As per the practitioner's discretion, refrain from treating any condition which might make it unsafe for the patient.
13. Tattoos, permanent makeup, scars or piercings in the treated area.
14. Exposure to investigational product within 3 months (or designated half-life) prior to enrollment.
15. Interventions, skin laser/light or another device for Acne treatment within the past 6 months.
16. Acne treatment with oral or topical medications within the last four weeks or their use during the course of the study.

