5.1 Screening Visit

5.1.1 Subject Enrollment

- During the first visit, the study investigator, and/or his designee, will screen the subject for eligibility to participate in the clinical study using the Inclusion/Exclusion criteria. During screening the study doctor will review the subject's medical history, and examine the subject's targeted area (facial acne vulgaris) to ensure that it meets the study criteria.
- If the subject has met the preliminary study criteria, an informed consent will be obtained from the subject, clearly indicating his/her understanding of the requirements and risks involved with study participation and other applicable treatment options.
- During the first visit, the investigator will ask women of child-bearing age for the date of their last period. If applicable, the investigator shall inquire about the form of contraceptive they use to confirm they meet the inclusion criteria. A urine pregnancy test will be performed.
- Male subjects should be informed that treatment in hair-bearing areas may result in some damage to the follicles and subsequent loss of hair, and as a consequence, hair growing zones should not be treated if a reduction of hair growth or ingrown hair is not desired.
- The investigator will perform an acne lesion count.
- Subjects will be asked to directly complete the CRF Acne Related Quality of Life Questionnaire worksheet which will be considered to be a source document.

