6.3.2 Adverse events

Adverse events will be assessed throughout the duration of the study. All adverse events will be categorized with respect to severity and device-relatedness.

The following skin reactions are an expected outcome related to treatment:

- Dryness
- Sloughing/flaking of skin
- Infection
- Presence of prolonged erythema
- Presence of prolonged edema
- Burn / Blistering
- Hyperpigmentation
- Hypopigmentation
- Contact dermatitis
- Pruritus/Scarring
- Herpes simplex virus outbreak

Reports of all adverse events by subjects and investigator will be documented in the source documents and will be recorded in the Adverse Events form.

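### For subjects with heat-triggered disease who receive prophylaxis, the synopsis permits treatment and section 4.2.2 excludes them; the two texts must be reconciled

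*Combined protocol and SAP*

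**What the plan says.** The group appears in two eligibility lists, and both are current text.

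- **Study Synopsis, Main Exclusion Criteria.** The bullet names people with a history of disease provoked by heat, with recurrent herpes as the example, and says that they "may be treated only following a prophylactic regimen". It stands under an exclusion heading but grants a conditional permission.
- **Section 4.2.2, Exclusion Criteria.** The list opens with "Any of the following will exclude the subject from the study". Item 5 reads "Patients with history of diseases stimulated by heat, such as recurrent Herpes Simplex in the treatment area" and carries no clause about prophylaxis.

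Three other places bear on how the lists are used. Section 4.2 introduces its own criteria with "Each subject will be evaluated by the Investigator to assess his/her suitability for entry into this study according to the following criteria". Section 5.1.1 says that the investigator or a designee "will screen the subject for eligibility to participate in the clinical study using the Inclusion/Exclusion criteria", without naming a section. Section 6.3.2 includes "Herpes simplex virus outbreak" among the skin reactions expected from treatment.

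**The concern.** One criterion is worded almost identically in two places, but the synopsis adds a condition that turns exclusion into permission. A site that reads the synopsis may enrol a subject whom section 4.2.2 excludes.

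Two things are at stake. The first is who is exposed: all subjects receive IPL to the face, and those assigned to the combination also receive RF with a target skin temperature of up to 40°C (section 5.2.2.2). The second is consistency. The synopsis describes the study as multi-center, and the safety evaluation in section 3.3 rests on the number and type of adverse events. If sites admit different subjects, the safety summary could mix populations selected under different rules. Whether a given enrolment counts as a protocol deviation would also depend on which page is consulted.

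**Working it through.** The plan gives no figure on this point, so the check is a comparison of texts.

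**Step 1: apply each text to each kind of subject** (otherwise eligible).

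| Subject | Synopsis | Section 4.2.2, item 5 | Agree? |
|---|---|---|---|
| No history of heat-triggered disease | Not barred | Not barred | Yes |
| History, no prophylaxis | Barred | Barred | Yes |
| History, prophylaxis given | May be treated | Barred | **No** |

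The disagreement is confined to the third row. It covers the whole class of heat-triggered disease, since herpes is only the named example in both texts.

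**Step 2: look for a rule that settles the third row.** Section 4.2 directs the investigator to its own list. Section 5.1.1 refers only to the inclusion and exclusion criteria, and both lists carry such a heading. No statement gives the body precedence over the synopsis. The other shared eligibility items do not show which list is the more recent. They also differ on prior acne treatment: 3 months in the synopsis, against 6 months for interventions and devices and four weeks for medications in section 4.2.2, items 15 and 16.

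**Step 3: look for a procedure behind the synopsis permission.** The protocol describes no prophylactic regimen beyond that one mention. Table 1 has no such step, and its concomitant-medication row starts at Visit 2. Section 5.1.3 allows the first treatment on the day of screening, with no word on how a regimen would fit before it.

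**Step 4: what it means for a site.** The synopsis wording is permissive. A site that turns such a subject away offends neither text. A site that admits one after prophylaxis follows the synopsis and breaks item 5. This describes the texts and is not a view on which rule is clinically right.

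**Step 5: size.** Section 4.1 gives the ceiling: "Up to 50 subjects with all skin phototypes shall be recruited by the investigator". The share with such a history, and the share of those given prophylaxis, are not stated. The number affected therefore lies somewhere between 0 and 50 and cannot be narrowed from the documents. Section 7.4 aims at an analysis set close to intent-to-treat for everyone enrolled, so the mismatch does not alter the primary analysis. It enters no alpha or power figure.

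**The case against.** The strongest reply is that the synopsis is a summary. It is headed as the main criteria only, and section 4.2 sends the investigator to a list with one clear rule. A site working from section 4.2 would face no ambiguity. This part stands: differing practice between sites is a possibility and not something the documents show. It does not remove the conflict. A summary may leave detail out, but this one adds a permission that the body does not contain.

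It can also be said that the missing prophylaxis procedure proves little. If section 4.2.2 governs, none is needed, and the treatment sections refer to a User Manual that is not among the documents. That is fair. The absence shows only that the protocol itself does not support the synopsis permission with a procedure.

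Three stronger readings are tempting, and the documents do not support them:

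- A reader might infer that the two texts are opposed for everyone with such a history. They agree wherever prophylaxis is not given.
- A reader might take the herpes entry in section 6.3.2 as a further contradiction. That section is a general list of possible skin reactions and is compatible with either rule. It shows only that the criterion concerns safety.
- A reader might size the problem by how far one outbreak would move an observed rate among 20 completers or 50 enrolled. That holds for any single event in a study of that size and does not measure this defect. Nor does the protocol set a criterion for a herpes rate.

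**Conclusion.** The point holds as an internal inconsistency in a safety-related eligibility rule. For a subject with heat-triggered disease who receives prophylaxis, the synopsis and section 4.2.2 give different answers, and the protocol has no precedence rule to decide between them. Sites could therefore treat the same kind of subject differently.

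Its reach is limited. Only that one group is affected, its size is unknown, and the statistical design and primary analysis are unchanged. The conclusion assumes that both lists are in force as printed in Amendment 2 and that no document outside those available settles the matter. It is worth correcting because the rule governs exposure of a group that the protocol itself singles out, and because the correction is cheap.

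**What to change.** Reconcile the Main Exclusion Criteria bullet in the synopsis with section 4.2.2, item 5, so that both carry the same rule. Which rule is a clinical decision for the sponsor.

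If the agreed rule admits such subjects, use the medical history already collected at screening (Table 1, section 5.1.1) to identify them when herpes outbreaks are listed. This needs no new assessment. If the agreed rule excludes them, aligning the wording is enough.

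The cost is a short change of wording, with sponsor agreement and IRB or ethics committee approval under section 9.7. No sample size, endpoint or analysis needs to change.

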3.1 Primary effectiveness endpoint

- Improvement in treated area appearance at 6 weeks after the last treatment as determined by a independent review.

Success criterion

The treatment will be considered successful if the appearance of Acne Vulgaris improves by at least 2 points on the 5-point Global Acne Assessment Score (GAAS) at 6 weeks follow-up compared to baseline in the study population. This will be determined by calculating the mean difference $GAAS-(\mu_d)$ between the GAAS at 6 weeks follow-up and the baseline scores in the study population. This improvement will also be further tested by two-sided Wilcoxon Signed-Ranks Test for Matched Pairs to establish that at 95% confidence level ($\alpha = 0.05$) there is a statistical significant evidence that mean difference scores obtained (μ_d) is not equal to zero.

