7.2 Study Hypothesis

The study hypothesis is that the treatment using Diamondpolar applicator followed by AC DUAL applicator and the AC DUAL applicator will improve the appearance of Acne Vulgaris by at least 2 points on the Global Acne Assessment Score (GAAS), at 6 weeks follow-up compare to baseline in the study population.

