7.4 Study Analysis

- All subjects will be evaluated for efficacy and safety data at baseline, during treatments and at 6-week post treatment visit.
- The analysis set will be as complete as possible and as close as possible to ensure it complies with the intent-to-treat principle for all enrolled subjects
- Subject demographics, baseline assessments, treatment parameters, treatment evaluations, follow-up assessments and reported adverse events will be summarized and analyzed using the following statistical tools:
 - All summary tables for quantitative parameters will display mean, standard deviation, median and applicable descriptive statistics. Correlations between variables will also be performed where applicable.
 - All summary tables for qualitative parameters will show counts, percentages and orders.
 - Number of missing data will be displayed on all tables where applicable.
 - Inter-rater reliability test will be performed to assess agreement between reviewers.
 - All statistical tests will be two-sided. The level of statistical significance for effectiveness analyses is 5% ($\alpha = 0.05$) for all tests of differences. Paired t-test and/or Wilcoxon Signed-

Ranks Test for Matched Pairs will be used to compare the evaluations at the baseline and post treatment sessions.

- For all primary and secondary end-point data generated in this study, applicable data analysis tools listed above will be used to determine if the study meets its efficacy and safety criteria.

8 Adverse Events

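### Section 3.1 sets success at a mean GAAS improvement of at least 2 points, but the only planned tests are against zero, so a significant p-value does not support the 2-point hypothesis

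*Combined protocol and SAP*

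**What the plan says.** The 2-point threshold appears in several places.

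- **Synopsis, Hypothesis:** "Improvement will be defined as achieving improvement of at least 2 points on the 5-point Global Acne Assessment Score (GASS) at FU". The sentence before it makes the claim for both regimens.
- **Synopsis, Primary endpoint:** "Acne Vulgaris improvement by at least 2 points on the Global Acne Assessment Score (GASS) from photographs 6 weeks following the last treatment". Neither synopsis entry names a unit (subject or group), a summary measure, or a proportion of subjects who must reach the threshold.
- **Section 3.1, rule for success:** "The treatment will be considered successful if the appearance of Acne Vulgaris improves by at least 2 points on the 5-point Global Acne Assessment Score", applied to the study population. The summary measure follows: "This will be determined by calculating the mean difference" between follow-up and baseline scores.
- **Section 3.1, test:** "This improvement will also be further tested by two-sided Wilcoxon Signed-Ranks Test for Matched Pairs", with the aim of showing that the mean difference "is not equal to zero".
- **Section 7.2:** the same 2-point hypothesis, "at 6 weeks follow-up compare to baseline in the study population".
- **Section 7.4:** two-sided tests at the 5% level, with a paired t-test and/or Wilcoxon test of baseline against post-treatment. Its last bullet says the tools listed there will decide whether the efficacy criteria are met.

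No section tests against 2 points, plans an interval for the mean change, or plans an analysis of the proportion improving by at least 2 points. No section says whether the mean criterion and the significance test must both be met.

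**The concern.** The hypothesis concerns a change of at least 2 points, while the test concerns a change of any size. A small p-value from the zero test says nothing about whether the improvement is near 2. Because 7.4 names these tests as the tools for judging the efficacy criteria, a significant result could be reported as meeting the primary endpoint when the mean is far below the threshold.

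Where the mean criterion is applied as written, it is a bare point estimate. An observed mean just above 2 would count as success with no statement of how far below 2 the true mean could lie. Section 3.6 says the primary endpoint has no concurrent control, so the 2-point threshold is the main thing separating a treatment claim from any before-after change.

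The synopsis adds a smaller problem. Its wording leaves room to report either a mean or a share of subjects, and the choice could be made after the data are seen.

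**Working it through.** **Inputs from the documents.** Threshold 2 points on a 5-point score; two-sided 5% level; null value zero (3.1, 7.4). Enrolment is up to 50, with 20 intended to complete on the amendment 2 parameters (Synopsis). Section 7.3 gives no effect size, SD, response rate or power, so there is no figure of the plan's own to reproduce.

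**Assumptions.** Change scores are whole numbers with a maximum of 4 (the scale is not printed). SD of change is 1 where an SD is needed. The 20 completers split equally, 10 per regimen (5.2 randomises between two treatments but gives no ratio).

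**1. How small a change makes the zero test significant?** If k subjects improve by 1 point and the rest do not change, the zeros drop out of the signed-rank test and the exact two-sided p-value is 2 × (1/2)^k.

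- k = 5: 2/32 = 0.0625, not significant.
- k = 6: 2/64 = 0.031, significant.

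Six subjects suffice whatever the sample size. The mean change is then:

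| n | Mean change (6/n) | Share improving by ≥ 2 points |
|---|---|---|
| 10 | 0.60 | 0% |
| 20 | 0.30 | 0% |
| 25 | 0.24 | 0% |
| 50 | 0.12 | 0% |

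**2. A uniform 1-point change, n = 20.** p = 2 × (1/2)^20 = 0.000002. The mean is 1.0, half the threshold, and no subject reaches 2 points.

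**3. Chance of a significant zero test at a true mean of 1.** Simulated with changes drawn from a normal distribution (mean 1, SD 1) and rounded:

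- n = 20: about 98%.
- n = 10: about 63% with the exact test and about 75% with the normal approximation.

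**4. Precision of the mean.** The 95% half-width is t × SD/√n.

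- n = 20: 2.093 × 1/√20 = 0.47.
- n = 10: 2.262 × 1/√10 = 0.72.

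For the interval to lie wholly at or above 2, the observed mean would have to be about 2.47 at n = 20 or 2.72 at n = 10.

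**5. Does it matter which reading of the synopsis is used?** Constructed examples, n = 20:

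- 19 subjects improve by 2 and one by 1: mean (38 + 1)/20 = 1.95, which misses the mean criterion, with 95% improving by at least 2.
- 7 improve by 4 and 13 by 1: mean (28 + 13)/20 = 2.05, which meets it, with 35% improving by at least 2.
- If the largest possible change is 3, a mean of 2 needs 3k + (20 − k) ≥ 40, so k ≥ 10, and at least half must improve by 2 or more.

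The mean and the proportion are therefore different quantities. Calling one a pass and the other a fail would need a required proportion, which the documents do not give.

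**The case against.** The strongest reply is that 3.1 already decides the matter. Success is determined by the mean difference and the Wilcoxon test is an addition, so a trial with a mean of 1 fails whatever its p-value. On that reading the zero test does no harm; in the constructed examples every mean of 2 or more was also significant. This is a fair reading of 3.1 taken alone, but 7.4 says its listed tools decide whether the criteria are met, and those tools include only tests of no change. Even if the mean criterion governs, the threshold is still judged without any statement of uncertainty.

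A reader might infer that the synopsis sets a per-subject responder rule that conflicts with the mean rule in 3.1, so that the two can reach opposite conclusions. The documents do not support that. The synopsis names neither a subject nor a mean, and sections 1.2, 3.1 and 7.2 all place the 2 points in the study population. Without a required proportion, a responder reading has no pass or fail that could oppose 3.1. The synopsis is incomplete rather than contradictory.

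A reader might also infer that the zero test would be significant in almost any trial with a 1-point change. That holds for about 20 subjects analysed together, but the hypothesis covers both regimens, and at an assumed 10 each the chance is nearer 63% to 75%.

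Finally, this is a pilot study, and 7.1 promises a final plan before data lock. That limits the seriousness and also provides the occasion for the repair.

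**Conclusion.** The concern stands in this form: the plan states a 2-point hypothesis and a 2-point success criterion, but its only tests are against zero and the 2-point threshold carries no measure of uncertainty. The mismatch is large. Six subjects improving by a single point make the zero test significant, at a mean of 0.30 among 20. That result needs only whole-number scores and the exact test, not an assumed SD. The power and interval figures rest on an assumed SD of 1 and, for n = 10, an assumed equal split of the 20 completers.

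The synopsis wording is a secondary defect: it omits the unit and the summary measure that 3.1 supplies. The point should be fixed, because the correction changes what may be concluded from the primary endpoint. It does not invalidate the design.

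**What to change.** - State the 3.1 mean rule in the same terms in the synopsis (Hypothesis and Primary endpoint), 3.1 and 7.2.
- For each regimen, report the mean GAAS change with its 95% CI alongside the 2-point threshold.
- Say in 3.1 and 7.4 that the test against zero shows only that some change occurred and does not by itself establish success.
- Say that if the interval includes values below 2, the report will not state that an improvement of at least 2 points was demonstrated.
- Report the proportion improving by at least 2 points, with an exact 95% CI, for each regimen as a supportive result.

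This needs wording changes and a few extra table rows, but no new data, and it fits the final plan promised in 7.1. The cost is that the 2-point claim will be shown with wide intervals: about ±0.47 at n = 20 and ±0.72 at an assumed 10 per regimen, SD 1 assumed.

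The sponsor's point-estimate criterion can remain as the success rule, since the interval governs only how strongly the result is described. Requiring a lower limit of at least 2 for success would be a much stricter rule. That is a design choice for the sponsor and is not needed to repair this defect.
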